### **Abnormal Laboratory Values or Vital Signs**

Protocol defined laboratory values and vital signs will be reported as AEs if the abnormal laboratory or vital sign result:

- Requires an adjustment in the study drug(s) or discontinuation of treatment;
- Requires additional testing, excluding repeat testing of the lab in question, or surgical intervention;
- Is associated with accompanying signs/symptoms that are not considered part of a pre-existing diagnosis or syndrome; or
- Is considered clinically significant by the Investigator.

If an abnormal laboratory value or vital sign is the result of an evaluation of clinical signs, symptoms, or suspected diagnosis during the conduct of the study, the signs/symptoms or diagnosis should be reported as an AE (or if appropriate, an SAE) only if clinically significant, and the associated laboratory value or vital sign should be considered additional information that must be collected on the relevant eCRF.

#### **12.1.5. Adverse Events of Special Interest**

[REDACTED]. The applicability of the finding in monkeys to humans is unknown. Notably, no adverse changes in serum chemistry markers (eg, creatinine and BUN) were observed with daily doses of EP547 as high as 225 mg for 1 week in healthy volunteers in the Phase 1 study. Any clinically meaningful new, worsening from baseline, or abnormal laboratory findings or symptoms suggestive of AKI (eg, 'blood urea increased' or 'protein urine present' AEs as identified by the SMQ 'Acute renal failure') will be considered AESI and should be reported on the SAE/AESI/Grade 3+ Report Form.

Acute renal failure is a syndrome characterized by a relatively rapid decline in renal function that leads to the accumulation of water, crystalloid solutes, and nitrogenous metabolites in the body. Other clinical features include increase in serum creatinine and urea nitrogen levels (azotemia) >0.5 and 10 mg/dL, respectively; oliguria; and changes in the rate of urine flow.

AESI must be reported to the Sponsor or designee using the SAE/AESI/Grade 3+ Report Form, according to the timelines described for SAEs in [Section 12.2.2](#).

## 12.2. Serious Adverse Events

### 12.2.1. Definition of a Serious Adverse Event

An SAE is any untoward medical occurrence, that at any dose:

- Results in death;
- Is life-threatening, ie, the subject is, in the opinion of the Investigator, at immediate risk of death from the event as it occurred (it does not include an event that, had it occurred in a more severe form, might have caused death);
- Requires hospital admission or prolongs hospitalization. Planned hospital admissions or surgical procedures for an illness or a disease that existed before administration of study drug, and for which the condition has not worsened since starting study drug, are not to be considered SAEs. Emergency room visits that are less than 24 hours will also not be considered SAEs;
- Results in persistent or significant disability or incapacity;
- Is a congenital anomaly/birth defect; or
- Is a medically significant event that, based on appropriate medical judgment, may jeopardize the subject and may require medical or surgical intervention to prevent one of the outcomes listed above.

Note: A distinction should be drawn between SAEs and severe AEs. Severity is a measure of the intensity of an AE, while the criteria for seriousness are indications of adverse subject outcomes for regulatory reporting purposes. A severe AE is not necessarily considered an SAE unless it fulfills one of the SAE criteria above. For example, a headache that persists for several hours may be considered a severe AE but not fulfill the criteria of an SAE. Conversely, a wound infection that may be considered minor could be an SAE if it prolonged hospitalization.

### 12.2.2. Reporting Serious Adverse Events

In the event of any SAE reported or observed after signing of the ICF until 30 days after the last dose of study drug, regardless of causality, site personnel will report it to [REDACTED] within 24 hours of the knowledge of the occurrence. If the Investigator becomes aware of an SAE any time after study completion and determines it is related to the study drug, the SAE must be reported to the Sponsor within 24 hours of the Investigator's knowledge of the SAE. To report an SAE, complete the study-specific SAE/AESI/Grade 3+ Report Form electronically in the electronic data capture (EDC) system for the study. This will trigger an email notification alert to the study team at [REDACTED] that an SAE has occurred. If the event meets serious criteria and it is not possible to access the internet, send an email to [REDACTED] safety team [REDACTED] or call the [REDACTED] [REDACTED] and fax/email the completed paper back-up SAE/AESI/Grade 3+ Report Form to [REDACTED] [REDACTED] within 24 hours of awareness. When the EDC system becomes available, the SAE information must be entered within 24 hours of the system becoming available. Incoming reports are reviewed during normal business hours.

Follow-up information to all SAEs should be submitted to the Sponsor, or designee, in the same timeframe as initial reports. Any supporting documentation (eg, medical records) sent to [REDACTED] with the SAE/AESI/Grade 3+ Report Form must have subject identifying information (eg, subject names, subject addresses, and medical records number) redacted by the site. All SAEs will be followed until resolution or medical stabilization (in cases where resolution would not be expected).

Reconciliation of SAE information in the EDC with the SAE information received and entered in the Argus Safety 8.2 database will be performed per the Data Management Plan.

**12.2.3. Reporting Serious and Unexpected Adverse Events Assessed as Related**

In accordance with applicable regulations and local laws, the Sponsor or designee will report all serious and unexpected AEs assessed as related to study drug by the Investigator and/or Sponsor, to the regulatory authorities within the required timeframe. The Investigator will be responsible for reporting this safety information to their IRBs/IECs, as required.

**12.2.4. Pregnancy**

Pregnancy in and of itself is not an AE, although pregnancies occurring in subjects or partners of male subjects are considered immediately reportable events. If a pregnancy occurs in a subject, study drug must be discontinued immediately. The pregnancy must be reported to [REDACTED] via email at [REDACTED] within 24 hours of the Investigator's knowledge of the pregnancy using the Pregnancy Reporting Form.

The Investigator will follow the pregnant woman until completion of the pregnancy, and must notify the Sponsor, or designee, of the outcome within 24 hours of the Investigator's knowledge of the pregnancy outcome. The Investigator will provide this information on the Pregnancy Reporting Form. This notification includes pregnancies resulting in live, "normal" births.

If the pregnant subject experiences an SAE during pregnancy, or the outcome of the pregnancy meets the criteria for immediate classification as an SAE (ie, spontaneous abortion [any congenital anomaly detected in an aborted fetus is to be documented], stillbirth, neonatal death, or congenital anomaly), the Investigator should follow the procedures for reporting SAEs [REDACTED] within 24 hours of the Investigator's knowledge of the event).

All neonatal deaths and congenital anomalies that occur within 30 days of birth (regardless of causality) should be reported as SAEs to the Sponsor. In addition, any infant death or congenital anomaly occurring after study completion that the Investigator suspects is related to the *in utero* exposure to the study drug should also be reported to the Sponsor.

**12.3. Data Monitoring Committee**

The DMC is an independent group of external experts who will review safety data during the conduct of the study, as outlined in the DMC charter. The DMC will make a determination of

relatedness for all AEs with CTCAE Grade 3 or higher. The DMC will also meet on an ad hoc basis when at least 3 AEs of CTCAE Grade 3 or higher have accrued or when there has been a single CTCAE Grade 4 or higher. Based on review of the data, the DMC will provide recommendations to the Sponsor on whether the nature, frequency, and/or severity of AEs associated with study drug warrant modification to the study protocol, suspension of dosing, or study termination.

#### **12.4. Medical History**

The Investigator will collect and review the subject's medical history to evaluate the subject's eligibility for study participation. The new onset of signs, symptoms, or other findings that occur from before signing of the ICF will be captured as medical history.

#### **12.5. Vital Signs**

Vital signs, including sitting systolic and diastolic blood pressure, pulse rate, oxygen saturation, body temperature, and respiratory rate, will be measured after at least 5 minutes of rest. Vital signs are to be performed predose if the dose is administered at the site.

Vital signs also include body weight, which should be measured with no shoes on and using a calibrated scale throughout the study.

#### **12.6. Physical Examinations**

Physical examinations will include, but are not limited to, an assessment of general appearance, skin, HEENT (head, eyes, ears, nose, throat), musculoskeletal, thyroid/endocrine, cardiovascular, chest/lung, neurologic, abdomen, and extremities/general body systems. Symptom directed physical examinations to assess clinically significant changes from Screening or any new signs or symptoms may be conducted at other visits as determined by the Investigator based on subject complaint.

For the decentralized model, the Investigator, assisted by the mobile nurse, will conduct physical examinations per protocol via telemedicine during a videoconference session.

#### **12.7. Standard 12-Lead Electrocardiograms**

Twelve-lead ECGs are to be performed with subjects in a supine position after at least 5 minutes of rest. An ECG is to be performed predose if the dose is administered at the site.

#### **12.8. Laboratory Evaluations of Safety**

Samples for the following laboratory tests will be collected after an overnight fast (at least 8 hours):

- Chemistry: sodium, albumin, ALP, bicarbonate, calcium, bile acids, corrected calcium, chloride, total and direct bilirubin, AST, ALT, BUN, urea, creatinine, magnesium, phosphorus, potassium, creatine phosphokinase (CPK), glucose, total cholesterol, triglycerides, high-density lipoprotein cholesterol (HDL-c), low-density lipoprotein cholesterol (LDL-c), lactate dehydrogenase (LDH), gamma-glutamyltransferase (GGT), and total protein

- Hematology: hemoglobin, hematocrit, white blood cell (WBC) count with differential (lymphocytes, neutrophils, monocytes, eosinophils, and basophils), red blood cell count, platelet count, and platelet volume. If a subject develops lymphopenia, blood lymphocytes will be tested to assess populations of circulating T cells (including CD4+ and CD8+ subtypes), B cells, and natural killer (NK) cells.
- Urinalysis: leukocyte esterase, nitrites, pH, protein, specific gravity, glucose, occult blood, ketones, bilirubin, urobilinogen, albumin, creatinine, sodium, chloride, and potassium; microscopic analysis is to be performed only if protein, leukocyte esterase, blood or nitrite is positive
- Coagulation: activated partial thromboplastin time (aPTT), INR, and prothrombin time (PT)
- Pregnancy testing: required for all females; serum test at Screening (Visit 1) and urine test for all other visits where pregnancy testing is required
- Thyroid function tests: TSH and free T4

The urine pregnancy test for female subjects will be conducted locally; all other planned laboratory evaluations of safety will be conducted at a central laboratory. Details for sample collection, processing, storage, and shipment will be provided in the Laboratory Manual.

### 12.9. Other Laboratory Evaluations

Samples for the following laboratory tests will be collected after an overnight fast (at least 8 hours):

- IgG4
- Serology: HIV, HAV, HBV, HCV, and HEV

Per exclusion criterion 6, subjects with uncontrolled viral hepatitis are not eligible to participate in this study. Active HAV infection is defined as a positive result for immunoglobulin M (IgM) anti-HAV or HAV ribonucleic acid (RNA). Current chronic HBV infection is defined as a positive result for hepatitis B surface antigen (HBsAg) or HBV deoxyribonucleic acid (DNA). Current chronic HCV infection is defined as a positive result for HCV antibody and HCV RNA at Screening. If HCV is cured, a negative HCV RNA confirmed within 1 year prior to Screening will be required. Active HEV infection is defined as a positive result for IgM anti-HEV or HEV RNA.

All serology laboratory evaluations will be conducted at a central laboratory. Details for sample collection, processing, storage, and shipment will be provided in the Laboratory Manual.

### 12.10. Transient Elastography

Transient elastography (FibroScan TE) is a validated, noninvasive technique used to assess hepatic stiffness (Corpechot 2016) that will be used to determine subject eligibility based on exclusion criterion 4. If an eligible historical TE within 6 months of Screening is not available, TE procedures will be conducted at study sites with the appropriate equipment and by adequately trained study site staff. Scheduling of the TE assessment should be within the Screening window (Day -28 to Day -1).

### **12.11. Partial Mayo Scoring Index (Subjects with Ulcerative Colitis Only)**

The Partial Mayo Scoring Index is a non-invasive questionnaire used as an outcome measure for clinical studies assessing therapies for UC (Lewis 2008). The index is composed of 3 categories (Bleeding, Stool Frequency, and Physician Assessment) that are each rated from 0 to 3 and summed to give a total score that ranges from 0 to 9. The Partial Mayo Scoring Index will be used to monitor disease stability during the course of the study.

### **12.12. Crohn's Disease Activity Index (CDAI) (Subjects with Crohn's Disease Only)**

The CDAI is a composite instrument used for evaluating the disease severity of CD that is scored on a scale from 0 to 1100 and includes abdominal pain, general well-being, complications, abdominal mass, anemia, and weight change. Subjects with CD can be divided into asymptomatic remission (CDAI <150), mild-to-moderate CD (150 to 219), moderate-to-severe CD (220 to 450), and severe-fulminant disease (>450) (Chen 2018). The CDAI will be used to monitor disease stability during the course of the study.

### **12.13. Subject Safety Guidelines**

#### **12.13.1. Potential Side Effects**

Safety results from the Phase 1 Study EP-547-101 did not reveal any safety trends, and there were no TEAEs assessed as expected with the use of EP547. Refer to the Investigator's Brochure for additional EP547 information regarding potential side effects.

#### **12.13.2. Overdose**

No specific information is available on the treatment of overdose of EP547. Additionally, there is no specific antidote to EP547. In a case of overdose, appropriate supportive measures should be employed.

#### **12.13.3. Monitoring and Management of Potential Drug-Induced Liver Injury**

Subjects will be assessed for potential DILI during both the Double-Blind Treatment Period and Open-Label Extension Period according to the consensus guidelines for clinical trials in adults with chronic cholestatic liver disease (Palmer 2020). Monitoring, interrupting, and stopping rules based on multiples of ULN, threshold values, baseline values, and/or nadir values of ALT, AST, ALP, and total bilirubin and liver-related symptoms are described in the algorithms for treatment-emergent hepatocellular and cholestatic DILI signals presented below.

Elevated ALP values should be confirmed to be of hepatic origin with GGT. Examples of liver-related symptoms include severe fatigue, nausea, new onset of or worsening of pruritus, right upper quadrant pain, immunologic reaction (eg, rash, >5% eosinophilia), and hepatic decompensation. If the algorithm calls for repeat blood tests, the tests are to be performed within 2 to 5 calendar days after receipt of laboratory values by the site for hepatocellular DILI signals and within 7 to 10 calendar days after receipt of laboratory values by the site for cholestatic DILI signals. ALT, AST, ALP, and total bilirubin, at a minimum, will be assessed as part of the repeat blood tests.

**Monitoring for Hepatocellular Injury**

The algorithm for monitoring and interrupting study drug for treatment-emergent hepatocellular DILI signals in subjects with a normal ALT baseline value is provided in [Table 5](#).

**Table 5: Algorithm for Monitoring and Interrupting Study Drug for Treatment-Emergent Hepatocellular DILI Signals in Subjects with a Normal ALT Baseline Value**

Treatment-Emergent ALT	Bilirubin	Liver-Related Symptoms	Action
ALT $\geq 5 \times$ ULN	Normal Gilbert's syndrome or hemolysis: No change in baseline total bilirubin	None	Repeat blood tests and monitor for symptoms.
ALT $\geq 8 \times$ ULN	Normal or elevated	None or present	Interrupt study drug and repeat blood tests. Study drug can be restarted if another etiology (not hepatocellular injury) is identified and abnormalities return to baseline levels.
ALT $\geq 3 \times$ ULN	Total bilirubin $\geq 2 \times$ baseline Gilbert's syndrome or hemolysis: direct bilirubin $> 2 \times$ baseline if baseline $> 0.5$ mg/dL	None or present	
ALT $\geq 5 \times$ ULN	Normal or elevated	Present	

ALT = alanine aminotransferase; DILI = drug induced liver injury; ULN = upper limit of normal.

The algorithm for monitoring and interrupting study drug for treatment-emergent hepatocellular DILI signals in subjects with an elevated ALT baseline value is provided in [Table 6](#).

**Table 6: Algorithm for Monitoring and Interrupting Study Drug for Treatment-Emergent Hepatocellular DILI Signals in Subjects with an Elevated ALT Baseline Value**

Treatment-Emergent ALT	Bilirubin	Liver-Related Symptoms	Action
ALT $\geq 3 \times$ baseline	Normal Gilbert's syndrome or hemolysis: No change in baseline total bilirubin	None	Repeat blood tests and monitor for symptoms.
ALT $\geq 5 \times$ baseline	Normal or elevated	None or present	Interrupt study drug and repeat blood tests. Study drug can be restarted if another etiology (not hepatocellular injury) is identified and abnormalities return to baseline levels.
ALT $\geq 2 \times$ baseline	Total bilirubin $\geq 2 \times$ baseline Gilbert's syndrome or hemolysis: direct bilirubin $> 2 \times$ baseline if baseline $> 0.5$ mg/dL	None or present	
ALT $\geq 2 \times$ baseline	Normal or elevated	Present	

ALT = alanine aminotransferase; DILI = drug induced liver injury.

Monitoring for Cholestatic Injury

The algorithm for monitoring and interrupting study drug for treatment-emergent cholestatic DILI signals is provided in [Table 7](#).

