**Table 7: Algorithm for Monitoring and Interrupting Study Drug for Treatment-Emergent Cholestatic DILI Signals**

Treatment-Emergent ALP	Bilirubin	Liver-Related Symptoms	Action
ALP $\geq 2\times$ baseline without alternative explanation	Normal Gilbert's syndrome or hemolysis: No change in baseline total bilirubin	None	Repeat blood tests and monitor for symptoms.
	Total bilirubin $\geq 2\times$ baseline Gilbert's syndrome or hemolysis: direct bilirubin $> 2\times$ baseline if baseline $> 0.5$ mg/dL	None or present	Interrupt study drug and repeat blood tests. Study drug can be restarted if another etiology (not cholestatic injury) is identified and abnormalities return to baseline levels.
	Normal or elevated	Present	
ALP $\geq 3\times$ baseline without alternative explanation	Normal or elevated	None or present	

ALP = alkaline phosphatase; DILI = drug induced liver injury.

In addition to the algorithms above, the Investigator may use clinical judgement to increase monitoring for DILI or interrupt or discontinue study drug as warranted for reasons of subject safety. An episode of DILI leading to hepatic decompensation in a study subject will result in permanent study drug discontinuation.

If a subject cannot return to the study site for a scheduled or unscheduled visit, or an immediate assessment is required, the use of a local laboratory is acceptable at the discretion of the Investigator. All local laboratory values obtained as part of DILI monitoring as well as their normal ranges are to be collected and entered into the clinical database.

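### In the DILI tables (Protocol Tables 5 to 7), an asymptomatic subject with bilirubin above normal but below twice baseline meets no row at enzyme levels where normal bilirubin requires a timed retest

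*Protocol*

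**What the plan says.** Protocol 12.13.3 gives three algorithms: Table 5 (normal baseline ALT), Table 6 (elevated baseline ALT) and Table 7 (ALP). The Synopsis repeats all three with the same conditions.

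In each table the first row applies to subjects without liver-related symptoms. Its bilirubin condition reads "Normal Gilbert's syndrome or hemolysis: No change in baseline total bilirubin", which is two lines of one cell: *Normal* for most subjects, and an unchanged total for those with Gilbert's syndrome or hemolysis. Its action is "Repeat blood tests and monitor for symptoms".

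The row that interrupts on bilirubin requires total bilirubin of at least 2× baseline. It has a second line beginning "Gilbert's syndrome or hemolysis: direct bilirubin", which sets a threshold of more than 2× baseline if baseline exceeds 0.5 mg/dL. The remaining rows interrupt at any bilirubin, either when symptoms are present or at the highest enzyme threshold.

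Repeats that the algorithm calls for are due "within 2 to 5 calendar days after receipt of laboratory values by the site for hepatocellular DILI signals". On the cholestatic side the window is longer, 7 to 10 days, and is counted from the same point. The text after Table 7 adds that "the Investigator may use clinical judgement to increase monitoring for DILI or interrupt or discontinue study drug as warranted".

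**The concern.** The first row and the bilirubin-interrupt row do not meet. Below the top enzyme threshold, a subject without symptoms gets a timed repeat if bilirubin is normal and an interruption if it has doubled. In between, the tables give no action.

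The order is the wrong way round for a safety rule. At the same ALT or ALP, the subject whose bilirubin is already above normal is the more worrying case, yet is the one with no required retest. At stake is a required early look at a possible liver signal in a placebo-controlled trial of a new drug.

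**Working it through.** There is no plan figure to reproduce. The check is to set the rows side by side and then work out who can fall between them and for how long.

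**Step 1. The rows (Protocol 12.13.3; TB = total bilirubin; subjects without Gilbert's syndrome or hemolysis).**

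| Table | Repeat: no symptoms, bilirubin normal | Interrupt: TB ≥2× baseline | Interrupt: symptoms present | Interrupt: any bilirubin or symptom state |
|---|---|---|---|---|
| 5 | ALT ≥5× ULN | ALT ≥3× ULN | ALT ≥5× ULN | ALT ≥8× ULN |
| 6 | ALT ≥3× baseline | ALT ≥2× baseline | ALT ≥2× baseline | ALT ≥5× baseline |
| 7 | ALP ≥2× baseline | ALP ≥2× baseline | ALP ≥2× baseline | ALP ≥3× baseline |

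The ALP rows apply where there is no alternative explanation for the rise.

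**Step 2. Run one subject through them.** Take ALT at 6× ULN, normal baseline ALT, no symptoms:

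- Bilirubin normal: repeat.
- Bilirubin above normal but <2× baseline: no row.
- Bilirubin ≥2× baseline: interrupt.
- Any of these with a symptom: interrupt.

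The pattern is the same at 5 and 7.9× ULN in Table 5, at 3, 4 and 4.9× baseline in Table 6, and at 2, 2.5 and 2.9× baseline in Table 7. It ends at 8× ULN, 5× baseline and 3× baseline respectively, where the unconditional interrupt row takes over. The bands are therefore ALT 5 to <8× ULN, ALT 3 to <5× baseline and ALP 2 to <3× baseline.

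**Step 3. Which bilirubin values fall in the gap.** The range runs from above ULN to <2 × baseline. It exists only if 2 × baseline > ULN, that is, baseline > ULN/2. The documents give no ULN; assume 1.0 to 1.3 mg/dL.

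- Baseline 0.5: upper end 2 × 0.5 = 1.0, so no gap.
- Baseline 0.8: above ULN to <1.6 mg/dL.
- Baseline 1.5: above ULN to <3.0 mg/dL.
- Baseline 2.0: above ULN to <4.0 mg/dL.

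Exclusion criterion 15a (Protocol 8.2) admits total bilirubin up to 2.0 mg/dL. Under the assumed ULN, a subject with a baseline of 1.5 or 2.0 is in the range with no rise in bilirubin at all.

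**Step 4. Gilbert's syndrome or hemolysis.** The direct-bilirubin line can be read in two ways:

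- (A) It replaces the total-bilirubin criterion for all these subjects.
- (B) It replaces it only when baseline exceeds 0.5 mg/dL; otherwise total ≥2× baseline still interrupts.

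The line also does not say which baseline it means. Take total bilirubin at 1.3× baseline, direct bilirubin unchanged from a baseline of 0.25 mg/dL, and no symptoms, with the enzyme in one of the bands. This subject meets no row under either reading. If total is instead ≥2× baseline, reading A gives no row and reading B interrupts. So the group exists, but its size depends on the reading.

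**Step 5. How long the wait could be.** Chemistry is drawn at every visit. Appendix A puts the visits at Days 8, 15, 22, 43, 64 and 85, so the intervals are 7, 7, 21, 21 and 21 days. With ±3 days at each end, 7 becomes 1 to 13 and 21 becomes 15 to 27. Assume 1 to 3 days from draw to receipt.

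- A required hepatocellular retest falls 1 + 2 = 3 to 3 + 5 = 8 days after the draw.
- A required cholestatic retest falls 1 + 7 = 8 to 3 + 10 = 13 days after the draw.
- After Weeks 3, 6 and 9, waiting for the nominal visit is later by 21 − 8 = 13 to 21 − 3 = 18 days (hepatocellular), or 21 − 13 = 8 to 21 − 8 = 13 days (cholestatic).
- After Weeks 1 and 2, the nominal 7-day visit falls between 1 day before and 4 days after the hepatocellular retest, and 1 to 6 days before the cholestatic one.
- After Week 12, the Follow-Up Visit comes 11 to 17 days after the last dose.

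**The case against.** The best case for leaving the tables alone is that the gap is narrow and covered in practice. The subject needs an enzyme rise inside a limited band, intermediate bilirubin and no liver-related symptom. The symptom list is broad: it includes nausea, severe fatigue and "new onset of or worsening of pruritus", and any one of them leads to interruption. The investigator may increase monitoring or interrupt, and local laboratories are allowed when assessment is urgent. Subjects are to be assessed "according to the consensus guidelines for clinical trials in adults with chronic cholestatic liver disease". Most investigators would probably retest.

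Much of this stands. It makes the waits in Step 5 worst cases: they assume a turnaround time and no unscheduled test. It does not close the gap. The discretion clause is permissive and sets no deadline, and the guideline sentence points to these same tables for the rules. Nor can *Normal* be stretched to cover anything short of doubling, because the tables write *Normal or elevated* where both are meant.

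A reader might go further and infer any of the following, none of which the documents support:

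- *That a stopping safeguard is missing.* No interruption or stopping rule is shown to be absent; what is missing is a required retest in asymptomatic subjects.
- *That every Gilbert's or hemolysis subject whose total bilirubin moves is unprotected.* That takes the no-change condition to the letter, so that even a small fall counts, and it adopts reading A of an ambiguous cell.
- *That the tables depart from the cited guidelines.* The guidelines are not among the documents, so this cannot be judged.

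**Conclusion.** The gap is real in the text of all three tables and their Synopsis copies. For subjects without Gilbert's syndrome or hemolysis it rests on no interpretation. For those with either condition it exists under both readings of the direct-bilirubin line, but its extent is uncertain.

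Its size is modest. The wait matters mainly for results from Weeks 3, 6 and 9; there is little or no delay after Weeks 1 and 2 on the nominal schedule. The bilirubin ranges depend on the assumed ULN. Frequency among about 58 subjects is unknown and probably low. The efficacy analysis is unaffected. The change is still worth making, because a timed safety rule should not require less monitoring when bilirubin is already abnormal.

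**What to change.** In the first row of Tables 5, 6 and 7 and the three Synopsis copies, change the bilirubin condition to: *Normal, or elevated but <2× baseline; Gilbert's syndrome or hemolysis: total bilirubin unchanged, or changed without meeting any interrupt row.* Add one sentence saying that when more than one row is met, the interrupt row governs. That sentence also settles an existing overlap: normal bilirubin without symptoms at ALT 8× ULN meets both the repeat row and an interrupt row.

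Do not write that any total bilirubin qualifies for repeat in Gilbert's syndrome or hemolysis. Under reading B, that would list for repeat only a subject whom the tables already interrupt. The wording above works under either reading and leaves every interrupt row as it is.

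The cost is one phrase in six places and one added sentence at the next amendment, plus a few extra repeat blood tests.
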